#### **7.9.3.1        *Analyses of Additional Efficacy Endpoints***

All categorical responder parameters (e.g., 6/12 Week CSBM Responder) and SBM within 24 Hours After First Dose, will be analyzed utilizing the same methods defined in Section 7.9.2.1.

All continuous change-from-baseline at each week endpoints and Treatment Satisfaction will be analyzed and summarized using the MMRM approach described in Section 7.9.1.1.

#### **7.9.4        *Randomized Withdrawal Period Endpoints***

For the RW Period, statistical analyses will be presented by treatment sequence (treatment sequences defined in Section 7.1.4).

The following endpoints will be calculated for the RW Period following the methods described for the primary and additional endpoints in Sections 7.9.1 and 7.9.3:

- Change from Baseline in Abdominal Score at Each Week
- Change from Baseline in Abdominal Bloating at Each Week
- Change from Baseline in Abdominal Discomfort at Each Week
- Change from Baseline in Abdominal Pain at Each Week
- Change from Baseline in CSBM Frequency Rate at Each Week
- Change from Baseline in SBM Frequency Rate at Each Week
- Change from Baseline in BSFS (Stool Consistency) at Each Week
- Change from Baseline in Stool Consistency at Each Week
- Change from Baseline in Percent of Days with Use of Rescue Medicine over the RW Period

#### **7.9.4.1            *Randomized Withdrawal Period Analyses***

All RW Period endpoints will be summarized for the RW Period only and for the Combined Treatment and RW Period using descriptive statistics and 95% CIs for each treatment sequence. No statistical inference will be performed.

### **7.10            *POSITIVE CONTROL***

Not applicable.

### **7.11            *SAFETY ANALYSIS***

For the Treatment Period, all safety analyses will be based on the Safety Population. For the RW Period and the combined 16-week Treatment-RW Period, the safety analyses will be performed using the RW Safety Population. The safety parameters will comprise adverse events (AEs), clinical laboratory parameters, and vital signs. For each safety parameter, the last nonmissing assessment made before randomization will be used as the baseline for all analyses of that safety parameter.

Treatment assignment for Safety summaries is based on the treatment the patient actually received. The ‘treatment actually received’ for patients who received treatment(s) other than their randomized treatment during the course of the trial will be defined as the treatment group in which the patient actually took the greatest number of doses.

Continuous variables will be summarized by number of patients and mean, SD, median, minimum, and maximum values. Categorical variables will be summarized by number and percentage of patients.

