#### **10.6.2 Clinical Laboratory Parameters**

Descriptive statistics for clinical laboratory values (in standard units) and changes from the baseline values at each assessment time point will be presented by treatment group for the Treatment Period and by treatment sequence for the Combined Treatment and RW Period, for each clinical laboratory parameter.

The number and percentage of patients with potentially clinically significant (PCS) post-baseline clinical laboratory values will be tabulated by treatment group for the Treatment Period and by treatment sequence for the RW Period and the Combined Treatment and RW Period. The criteria for PCS laboratory values will be detailed in the SAP. The percentages will be calculated relative to the number of patients with available non-PCS baseline values and at least 1 assessment in the corresponding post-baseline period. The numerator will be the total number of patients with available non-PCS baseline values and at least 1 PCS value in the corresponding post-baseline period. A supportive listing of patients with PCS post-baseline values will be provided, including the PID number, trial center, and baseline and post-baseline values. A listing of all AEs for patients with PCS laboratory values will also be provided.

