#### **7.11.1            *Adverse Events***

Adverse events will be coded by system organ class and preferred term using the MedDRA dictionary, version 21.0.

An AE that occurs during the Treatment Period will be considered a treatment-emergent adverse event (TEAE) if it was not present prior to the date of the first dose of double-blind study drug or was present prior to the date of the first dose but increased in severity during the Treatment Period. If more than 1 AE was reported before the first dose of double-blind study drug and coded to the same preferred term, the AE with the greatest severity will be used as the benchmark for comparison with the AEs occurring during the Treatment Period that were also coded to that preferred term.

An AE that occurs on or after the date of the first dose of the double-blind study drug for the RW Period will be considered a TEAE for the RW Period (RW TEAE) if it was not present prior to the date of the first dose of double-blind study drug of the Treatment Period or was present prior to the date of the first dose of double-blind study drug for the Treatment Period but increased in severity on or after the date of the first dose of the double-blind study drug for the RW Period. An AE that occurs more than 1 day after the last dose of study drug in the RW Period will not be considered a RW TEAE.

An AE that occurs on or after the date of the first dose of the double-blind study drug for the RW Period will be considered a newly emergent adverse event (NEAE) for the RW Period if it was not present prior to the date of the first dose of the double-blind study drug for the RW Period or was present prior but increased in severity after receiving RW period double-blind study drug. An AE that occurs more than 1 day after the last dose of double-blind study drug will not be counted as an NEAE.

The period in which a serious adverse event (SAE) occurred will follow the methods defined above for TEAEs, RW TEAEs, and NEAEs. [Table 7.11-1](#) summarizes the classification of AEs.

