### 7.11.2 Clinical Laboratory Parameters

Descriptive statistics for clinical laboratory values (in SI units) and changes from the baseline values at each assessment time point will be presented by treatment group for Treatment Period and by treatment sequence for the RW Period. The End of Treatment is the last non-missing postbaseline value in the Treatment Period; End of study is the last non-missing postbaseline value. The hematology and chemistry laboratory parameters listed in Section 5.4.5 will be summarized.

Clinical laboratory test values will be potentially clinically significant (PCS) if they meet either the low or high PCS criteria listed in Table 7.11-2. The number and percentage of patients with postbaseline PCS clinical laboratory values will be tabulated by treatment group for the Treatment Period and by treatment sequence for the RW and Treatment-RW Periods. The percentages will be calculated relative to the number of patients with non-PCS baseline values and at least 1 assessment in the corresponding postbaseline period. A supportive listing of patients with postbaseline PCS values will be provided, including the PID number, trial center, and baseline and postbaseline values. A listing of all AEs for patients with PCS clinical laboratory values will also be provided. The PCS flags will be derived flags (not from the clinically significant laboratory tests reported as AEs by trial centers).

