### 7.11.3 Vital Signs

Descriptive statistics for body weight and vital signs (oral temperature, respiratory rate, systolic and diastolic blood pressure, and pulse rate) and changes from baseline values at each visit will be presented by treatment group for the Treatment Period and by treatment sequence for the Treatment-RW period. The End of Treatment is the last non-missing postbaseline value in the Treatment Period; End of study is the last non-missing postbaseline value.

Vital sign values will be considered PCS if they meet both the observed-value criteria and the change-from-baseline criteria listed in [Table 7.11-3](#). The number and percentage of patients with postbaseline PCS vital signs will be tabulated by treatment group for the Treatment Period and by treatment sequence for the RW Period and the Treatment-RW Period. The percentages will be calculated relative to the number of patients with nonmissing baseline values and at least 1 assessment in the corresponding postbaseline period. A supportive listing of patients with postbaseline PCS values will be provided, including the PID number, trial center, and baseline and postbaseline values.

A listing of all AEs for patients with PCS vital sign values will also be provided.

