**Table 9.1-1 Visit Time Windows for Safety Analysis**

Derived Visit	Scheduled Test / Visit Daya	Window
Baseline	Day 1	Days $\leq$ 1
Week 4 (Day 29) Visit	Day 29	Days [2, 43]
Week 8 (Day 57) Visit	Day 57	Days [44, 71]
Week 12 (Day 85) Visit	Day 85	Days $\geq$ 72 but prior to RW Day 1
End of Treatment Period b	End of Treatment Period Visit	
Week 16 (RW Day 29) Visit	RW Day 29	Days $>$ RW Day 1
End of Trial	End of Trial Visit	

a Relative to the date of randomization or first RW dose; Day 1 = the day of randomization; RW Day 1 = the day of first RW dose.

b “End of Treatment Period/End of Trial” will be presented in analysis tables for safety parameters, including ECG, clinical laboratory, and vital signs.

Test/Visit Day will be calculated as follows: test/visit date – date of randomization or date of first RW dose + 1.

If there are multiple values available for the same Visit, the data with the latest date for that visit will be utilized for summary.

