## **9.5 REPEATED OR UNSCHEDULED ASSESSMENTS OF SAFETY PARAMETERS**

If a patient has repeated assessments prior to the start of double-blind study drug, then the results from the final non-missing assessment made prior to the start of the double-blind study drug will be used as baseline. If end-of-trial assessments are repeated or if unscheduled visits occur, the last non-missing post baseline assessment will be used as the end-of-trial assessment for generating summary statistics. However, all post-baseline assessments will be used for PCS value determination as described above and all assessments will be presented in the data listings.

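### The RW-only PCS tables for laboratory values and vital signs use only a Day 1 reference, so they count carried-over abnormalities and can miss changes that follow the RW switch

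*SAP*

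**What the plan says.** SAP 7.11 fixes one baseline per safety parameter: "the last nonmissing assessment made before randomization will be used as the baseline for all analyses of that safety parameter". The Week 12 laboratory tests and vital signs are also scheduled ahead of a randomization, so the word alone is ambiguous. Two places settle it. SAP Table 9.1-1 gives the baseline window as Days ≤ 1 and separates the two dates: "Day 1 = the day of randomization; RW Day 1 = the day of first RW dose". SAP 9.5, on repeated assessments, says that "results from the final non-missing assessment made prior to the start of the double-blind study drug will be used as baseline".

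PCS laboratory values are tabulated "by treatment sequence for the RW and Treatment-RW Periods" (SAP 7.11.2) and PCS vital signs "by treatment sequence for the RW Period and the Treatment-RW Period" (SAP 7.11.3). The RW-only vital-sign table comes from the SAP; protocol 10.6.3 plans only the Treatment Period and the combined period. The laboratory percentage is taken "relative to the number of patients with non-PCS baseline values and at least 1 assessment in the corresponding postbaseline period", and protocol 10.6.2 puts in the numerator patients who also have "at least 1 PCS value in the corresponding post-baseline period". The vital-sign flag in SAP Table 7.11-3 combines an observed value with a change from baseline; for weight, a change of at least 7% is the only criterion. Status at Week 12 enters none of these rules.

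Adverse events are treated differently. SAP 7.11.1 and Table 7.11-1 define an RW TEAE against the screening and pretreatment periods. They also define a second class by which an event "will be considered a newly emergent adverse event (NEAE) for the RW Period" when it is new or worse since the first RW dose.

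**The concern.** Treatment changes on RW Day 1 in two of the three sequences. Protocol 5.2 gives the RW Period the job of showing rebound or other withdrawal effects, and patients in the Placebo-290 sequence first receive linaclotide in it. A reader will take an RW-only PCS table to describe what happened in those four weeks. With a Day 1 reference it describes the patient's state at Week 16 relative to before the trial, so it mixes what was brought into the RW Period with what arose during it.

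The same applies to the RW change-from-baseline summaries of laboratory values in SAP 7.11.2, which show cumulative 16-week change. The SAP recognises this distinction for adverse events and gives no reason for leaving it out for derived flags.

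**Working it through.** The documents give no PCS rate or RW count, so there is no figure of the plan's to reproduce. The check applies the written rules to possible patient courses.

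**Laboratory flags** (1 = PCS). The SAP rule is non-PCS at Day 1 and PCS at Week 16. The newly emergent rule is non-PCS at Week 12 and PCS at Week 16.

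| Day 1 / Week 12 / Week 16 | SAP rule, RW Period | Newly emergent |
|---|---|---|
| 0 / 0 / 1 | counted | counted |
| 0 / 1 / 1 | counted | not counted |
| 0 / 1 / 0 | not counted | not counted |
| 1 / 0 / 1 | not counted | counted |
| 1 / 1 / 1 | not counted | not counted |

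The rules differ in the second and fourth rows: a carried-over case is counted, and a recurrence after a normal Week 12 value is not.

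**Vital signs and weight** (Table 7.11-3 criteria, illustrative values).

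- Weight 80 / 74 / 74 kg: 74/80 − 1 = −7.5% from Day 1, so it is flagged in the RW Period. Change during that period is 74/74 − 1 = 0.0%.
- Weight 80 / 84 / 78 kg: 78/84 − 1 = −7.1% during the RW Period, but 78/80 − 1 = −2.5% from Day 1, so it is not flagged.
- Systolic pressure 100 / 115 / 90 mm Hg: the observed value meets the low limit of 90. The fall is 25 from Week 12 but only 10 from Day 1, short of the required 20, so it is not flagged.

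**Effect on the contrast.** Let p be the proportion PCS by Week 12, q the proportion of those persisting to Week 16, and r the proportion newly PCS in the RW Period among the rest, taking all patients as non-PCS at Day 1. The expected RW count under the SAP rule is

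n × [p×q + (1 − p)×r],

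of which n×p×q is carried over. Rerandomization makes p equal in expectation in 290-290 and 290-Placebo. If q is also equal, the carried-over term cancels in the difference between those sequences. It still raises both rates, pulls their ratio toward 1 and adds noise. Placebo-290 has its own p, with no matching sequence.

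**Illustration on assumed rates.** Of 300 linaclotide patients split 1:1, each linaclotide sequence has at most 300/2 = 150; Placebo-290 has at most about 300. Assumed, not from the documents: p = 1% to 5%, q = 30% to 80%, r = 1%.

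- Low end: 150 × (0.01×0.3 + 0.99×0.01) = 1.9 expected flags per parameter, of which 150×0.01×0.3 = 0.45 carried over, or 23%.
- High end: 150 × (0.05×0.8 + 0.95×0.01) = 7.4, of which 150×0.05×0.8 = 6.0 carried over, or 81%.
- Newly emergent count: 150×0.99×0.01 = 1.5 to 150×0.95×0.01 = 1.4.

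At an assumed 80% completion (n = 120) the counts shrink and the shares do not change, because n cancels. The width of the range shows how little can be said about size.

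**The case against.** The Day 1 baseline is a defensible choice. The RW Period is meant partly to detect rebound, which protocol 5.2 frames as worsening from baseline. Protocol 10.4.9 keeps the pretreatment baseline for RW efficacy endpoints, and RW TEAEs use the same reference. Substituting Week 12 would create its own blind spots. A patient at −4% weight at Week 12 and −8% at Week 16 has changed by only 0.92/0.96 − 1 = −4.2% in the RW Period and would drop out of the table. A patient already PCS at Week 12 who worsens would drop out too. This stands, and it rules out replacing the Day 1 tables.

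Much can also be found elsewhere. Under protocol 8.2.1.2.3 and 8.2.1.3, clinically significant laboratory and vital-sign abnormalities are reported as adverse events and so reach the NEAE tables. The PCS listings show baseline and postbaseline values, so a carried-over case can be traced by hand. This also stands. The gap is limited to derived flags not reported as adverse events, and to what the tables themselves show.

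A reader might infer that abnormalities which emerged on linaclotide are charged to RW placebo. The documents do not support that: the columns are the sequences in SAP 7.1.4, and each name carries both treatments. A reader might also infer that the tables cannot show anything about withdrawal. That fails because 290-290 is a concurrent rerandomized control for 290-Placebo.

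**Conclusion.** The point holds as a gap in the descriptive safety summaries. The RW-only PCS tables count abnormalities that arose in Weeks 1-12 and persist, and can miss changes confined to the RW Period. Rates are inflated and the linaclotide withdrawal contrast is diluted; with equal persistence in the two sequences it is not systematically biased. The lack of a matched comparator matters most for Placebo-290.

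No firm count can be attached. It would be tempting to treat nearly every Week 12 weight flag as repeating at Week 16. For example, 130 patients per sequence and a 2% Week 12 rate give 0.02 × 130 = 2.6 false cases. But the sequence size, the rate and the full persistence this needs are all assumptions. The mechanism follows from the text; its size does not.

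No RW inference is planned and no efficacy result depends on these tables, so this is a desirable addition rather than a necessary correction.

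**What to change.** Keep the Day 1-referenced tables for the Treatment, RW and combined periods. Add to SAP 7.11.2 and 7.11.3, for the RW Period by treatment sequence, a second set referenced to the last non-missing assessment before the first RW dose:

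- newly emergent PCS counts, with patients not PCS at that assessment as the denominator;
- for vital signs and weight, the change criteria of Table 7.11-3 measured from that assessment;
- descriptive summaries of change from that assessment.

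This gives derived flags the same pairing that Table 7.11-1 gives adverse events. The retained Day 1 tables continue to show cumulative change.

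The cost is a few sentences in the SAP and a few more descriptive tables. Laboratory tests, vital signs and weight are already scheduled at the Week 12 Visit before rerandomization, with the first RW dose the next day, so no new data are needed.

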#### **7.11.1            *Adverse Events***

Adverse events will be coded by system organ class and preferred term using the MedDRA dictionary, version 21.0.

An AE that occurs during the Treatment Period will be considered a treatment-emergent adverse event (TEAE) if it was not present prior to the date of the first dose of double-blind study drug or was present prior to the date of the first dose but increased in severity during the Treatment Period. If more than 1 AE was reported before the first dose of double-blind study drug and coded to the same preferred term, the AE with the greatest severity will be used as the benchmark for comparison with the AEs occurring during the Treatment Period that were also coded to that preferred term.

An AE that occurs on or after the date of the first dose of the double-blind study drug for the RW Period will be considered a TEAE for the RW Period (RW TEAE) if it was not present prior to the date of the first dose of double-blind study drug of the Treatment Period or was present prior to the date of the first dose of double-blind study drug for the Treatment Period but increased in severity on or after the date of the first dose of the double-blind study drug for the RW Period. An AE that occurs more than 1 day after the last dose of study drug in the RW Period will not be considered a RW TEAE.

An AE that occurs on or after the date of the first dose of the double-blind study drug for the RW Period will be considered a newly emergent adverse event (NEAE) for the RW Period if it was not present prior to the date of the first dose of the double-blind study drug for the RW Period or was present prior but increased in severity after receiving RW period double-blind study drug. An AE that occurs more than 1 day after the last dose of double-blind study drug will not be counted as an NEAE.

The period in which a serious adverse event (SAE) occurred will follow the methods defined above for TEAEs, RW TEAEs, and NEAEs. [Table 7.11-1](#) summarizes the classification of AEs.

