### Treatment-emergent Adverse Event

A treatment-emergent AE (TEAE) is an event that emerges, or a preexisting event that worsens, any time after administration of the first dose of study drug (Day 1).

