### **10.6.1               Adverse Events**

Adverse Event Verbatim Terms will be coded in the EDC system against the most current version of MedDRA available at the start of the trial (or newer).

An AE that occurs during the Treatment Period will be considered a treatment-emergent AE (TEAE) for the Treatment Period if it was not present prior to the date of the first dose of double-

blind study drug, or was present prior to the date of the first dose but increased in severity during the Treatment Period.

Similarly, an AE that occurs on or after the date of the first dose of double-blind study drug for the RW Period (up to 1 day after the last dose of double-blind study drug) will be considered a TEAE for the RW Period if it was not present prior to the date of first dose of study drug for the Treatment Period, or was present prior to the date of the first dose for the Treatment Period but increased in severity on or after the date of the first dose for the RW Period.

An AE that occurs on or after the date of the first day of dosing in the RW Period (up to 1 day after the last dose of double-blind study drug) will be considered a newly-emergent adverse event (NEAE) for the RW Period if it was not present prior to the date of the first calendar day of dosing in the RW Period, or was present prior to the date of the first calendar day of dosing in the RW Period, but increased in severity on or after the date of the first calendar day of dosing in the RW Period.

If more than one AE is reported prior to the first dose of double-blind study drug and coded to the same preferred term, the AE with the greatest severity will be used as the benchmark for comparison with the AEs occurring during the Treatment and RW Periods that were also coded to that preferred term. An AE that occurs more than 1 day after the last dose of double-blind study drug will not be counted as a TEAE or NEAE.

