**Table 7.11-1 Adverse Event Classification**

Type of AE	Reference Period for Baseline	Starting Point of Period	Ending Point
TEAE	Screening+ pretreatment	First dose during treatment period	Earlier of day after last dose of Trt period & day before first dose of RW period
RW TEAE	Screening+ pretreatment	First dose during RW period	Day after date of last dose of RW trt
NEAE	Screening+ pretreatment+ treatment	First dose during RW period	Day after date of last dose of RW trt

The number and percentage of patients in each treatment group who experience TEAEs will be summarized. For the Treatment Period, TEAEs will be summarized for each treatment group by system organ class and preferred term; by system organ class, preferred term, and severity; and by system organ class, preferred term, and relationship to study drug. The same summaries will be provided for each treatment sequence for the RW Period (RW TEAEs and NEAEs). For the Treatment-RW Period, TEAEs will be summarized for each treatment sequence by system organ class and preferred term only. If a patient has more than 1 AE coded to the same preferred term, the patient will be counted only once for that preferred term by identifying those TEAEs with the greatest severity and the closest relationship to study drug for the summarization by severity and by relationship to the study drug, respectively.

For the Treatment Period, the incidence of common ( $\geq 2\%$  of patients in any treatment group) TEAEs, on-therapy serious adverse events (SAEs), and AEs leading to premature discontinuation of study drug will be summarized by preferred term and treatment group, sorted in decreasing frequency. The above summaries will also be provided for the RW Period by treatment sequence. In addition, the incidence of on-therapy SAEs that led to death will be summarized.

For the Screened Population, listings will be presented for patients who died, patients with SAEs, and patients with AEs leading to premature discontinuation, if any.

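### The TEAE severity benchmark has no condition that the pre-dose event be ongoing, so a new on-drug episode (or SAE) can be left out of the incidence tables; the likely effect is small

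*SAP*

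**What the plan says.** SAP 7.11.1 counts a Treatment Period AE as a TEAE in two cases: it was absent before the first double-blind dose, or it was already there and then became more severe. A further sentence sets the comparator: "the AE with the greatest severity will be used as the benchmark for comparison with the AEs occurring during the Treatment Period" sharing its preferred term. The condition that opens this sentence is "If more than 1 AE was reported before the first dose of double-blind study drug and coded to the same preferred term", so it is written for several earlier AEs. SAP Table 7.11-1 gives the reference period for a TEAE as "Screening+ pretreatment", which by the Schedule of Evaluations can be up to 21 + 21 days.

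On serious events, SAP 7.11.1 adds: "The period in which a serious adverse event (SAE) occurred will follow the methods defined above for TEAEs, RW TEAEs, and NEAEs". The incidence of on-therapy SAEs is then tabulated, and patients with SAEs are listed for the Screened Population.

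The protocol speaks to this twice. Section 8.2.1.1 defines a TEAE as "an event that emerges, or a preexisting event that worsens, any time after administration of the first dose of study drug". Section 10.6.1 has the two-part test and benchmark found in the SAP, and extends the latter to both periods: "benchmark for comparison with the AEs occurring during the Treatment and RW Periods that were also coded to that preferred term".

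**The concern.** The benchmark compares separately recorded AEs that share a preferred term; it does not follow one event over time. With no condition that the earlier AE be ongoing at first dose, a mild diarrhea episode that resolved in the Pretreatment Period can cancel a new mild episode on study drug.

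The setting makes this plausible. Bisacodyl is available in the Pretreatment Period (Protocol Appendix 2). Exclusion 18 screens out loose stools only among spontaneous bowel movements, so laxative-related ones do not trigger it. Exclusion 19 bars rescue use on the day before and the day of randomization, so such an episode would probably be over by first dose. Pretreatment AEs of randomized patients go onto the eCRF (Protocol 8.2.1.3), so the benchmark has data to act on.

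TEAE and on-therapy SAE incidence are main safety outputs. Any loss is proportional to on-drug incidence, so for diarrhea it falls mostly on linaclotide and narrows the difference between arms. Severity is not seriousness (Protocol 8.2.1.2.1), so a new SAE can carry the same grade as an earlier non-serious AE of its term.

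**Working it through.** The documents attach no figure to this rule, so there is nothing of theirs to reproduce. The check has three parts.

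**1. Which cases are dropped.** Take a resolved pre-dose AE and a new post-dose AE of the same term, each mild, moderate or severe: 3 × 3 = 9 pairs.

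- Benchmark reading (SAP 7.11.1, Protocol 10.6.1): the new AE counts only if it is more severe. Six of 9 pairs are dropped: mild/mild, moderate/mild, moderate/moderate, severe/mild, severe/moderate and severe/severe (pre-dose/post-dose).
- Protocol 8.2.1.1, with a new onset taken as an event that emerges: 0 of 9 are dropped.

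**2. Size for diarrhea.**

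Inputs from the documents: diarrhea TEAE incidence of 19.8% on linaclotide and 3.0% on placebo in the two registration trials (Protocol 3.3), and 300 patients per arm.

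Assumed inputs: a share p = 1% to 5% of patients with a pre-dose AE of the same term; a share s = 70% to 100% whose worst on-drug episode is no more severe than the pre-dose one; and independence of pre-dose and on-drug events.

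Loss in percentage points = incidence × p × s.

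| | Low (p = 0.01, s = 0.7) | High (p = 0.05, s = 1) |
|---|---|---|
| Linaclotide | 19.8 × 0.007 = 0.14 | 19.8 × 0.05 = 0.99 |
| Placebo | 3.0 × 0.007 = 0.02 | 3.0 × 0.05 = 0.15 |
| Linaclotide patients of 300 | 0.42 | 2.97 |
| Placebo patients of 300 | 0.06 | 0.45 |
| Difference between arms (16.8 with no loss) | 16.8 × 0.993 = 16.7 | 16.8 × 0.95 = 16.0 |

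A rough anchor for p is the 3.0% placebo rate, from trials with treatment periods of 12 and 26 weeks. The pre-dose window is at most 42 days, or 6 weeks. Scaling by time gives 3.0 × 6/26 = 0.7% to 3.0 × 6/12 = 1.5%. The linaclotide loss is then 19.8 × 0.0069 × 0.7 = 0.10 to 19.8 × 0.015 × 1 = 0.30 points, or about 0.3 to 0.9 of 300 patients. This scaling ignores bisacodyl use, which could raise p.

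**3. SAEs.** The earlier trials report 0.7% on linaclotide and 1.1% on placebo. At 300 per arm that is 300 × 0.007 = 2.1 and 300 × 0.011 = 3.3 events. A loss needs a pre-dose AE of the same term and at least equal severity, so it should be rare, but each loss is a whole event from a very small count.

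**The case against.** The exclusion is not spelled out. Protocol 8.2.1.3 requires onset and duration for each episode of an intermittent AE. Read episode by episode, a new onset was not present before first dose and passes the first part of the test. The benchmark sentence literally covers only more than one pre-dose AE, so it reaches a single earlier episode only by implication. This stands as a limit on how firmly the rule can be stated. It does not remove the point: if every new onset counted anyway, choosing the worst of several pre-dose AEs would serve little purpose, and it would be odd to suppress after two earlier AEs but not after one. Two programmers could produce different tables.

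A reader might infer that the SAP departs from the protocol. It does not: Protocol 10.6.1 has the same rule. The conflict is between two protocol sections, and the SAP inherits it.

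A reader might also infer that SAEs could vanish from the report. They could not, because patients with SAEs are listed whatever their TEAE status. The SAE sentence can even be read as assigning period only, with no severity filter. The exposure is limited to the incidence table, on the reading that on-therapy follows the TEAE rule; the SAP gives no separate definition.

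Other features limit the effect. Incidence is counted per patient, so one more severe on-drug episode restores the patient. SAP 9.7 sets missing severity to mild before dosing and severe after, which favors counting. Exclusion 18 reduces diarrhea in the two weeks before randomization.

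**Conclusion.** The point holds in a limited form. As most naturally programmed, the benchmark leaves out a new post-dose episode no more severe than a resolved pre-dose one of the same term, which sits poorly with Protocol 8.2.1.1.

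Under assumed pre-dose rates of 1% to 5%, the diarrhea loss is roughly 0.1 to 1.0 points on linaclotide and at most 0.15 on placebo. The time-scaled estimate is about one patient per arm or fewer. These sizes rest on assumed p and s, on independence, and on the earlier trials' incidences; they would be larger if patients with pre-dose episodes are more prone to on-drug ones.

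The documents do not support reading this as a material distortion of the safety profile. It is a small undercount, weighted toward the drug arm, that is cheap to remove.

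**What to change.** In SAP 7.11.1:

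- Count an AE with onset on or after the first Treatment Period dose, within the Table 7.11-1 window, as a TEAE. Apply the severity benchmark only to AEs of the same term still ongoing at first dose, and say that this holds for one such AE as well as for several.
- Define on-therapy SAEs by onset date, with no severity filter.
- For RW TEAEs, remove only the benchmark against resolved pre-dose events. Keep the present inclusion of events that began in the Treatment Period and carried over. A pure onset rule would drop those and make RW TEAEs nearly the same as NEAEs.

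Reconcile Protocol 8.2.1.1 with 10.6.1 so that both documents carry one definition.

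The cost is a few sentences and a programming change; onset dates per episode are already collected. The downside is that TEAE rates rise slightly in both arms and some background recurrences are counted.
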